8.1.1 INCLUSION CRITERIA

Patients to be included in this phase 1 of this study must fulfil all of the following criteria:

- Adult patients >18 years old (indicated from patient details) admitted to RFH ITU from the 1st of April 2020 until the 30th of October 2020;
- Intubated and ventilated (indicated from documentation in notes);
- Ventilated with anaesthetic machine during their admission (as suggested by daily nursing observation charts and daily review sheets in the notes of ICU clinicians and physiotherapists).

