9 STUDY PROCEDURES

9.1 PHASE 1 PROCEDURES: quantitative cohort study

9.1.1a - Retrospective data collection

The quantitative phase of this study aims to broadly examine the impact of using anaesthetic machines for ventilation of COVID-19 positive patients.

Important note: current inability to access the patient notes and observation charts (access to notes is requiring a quarantine period once a patient has been discharged from ITU; this is currently 2 weeks) may lead to partial availability of the data described in the endpoints section. Anecdotal evidence from discussions with nursing staff suggests that it may not be possible to tell from the documentation which patients were ventilated with AnMach versus a conventional ITU ventilator. This issue can only be addressed following accessing some of the observation charts that have been processed and released from quarantine. At this moment we can hypothesise two options:

Option I, we can label the charts as AnMach use: It will be possible to perform a clinical outcomes and adverse events comparison between patients identified as being ventilated by AnMach and those

identified as being ventilated by conventional ICU ventilators. In this case (less likely) we will request a study amendment after having access to the chart and being sure we can achieve this. We will also request an amendment in case of a second surge of COVID19 for the prospective data collection.

Option II, we cannot distinguish which device was used to ventilate the patients: adverse events possibly linked to AnMach will be recorded from charts of all patients admitted to 2NA and main recovery between the 1st April and the 1st of June 2020. We will also review Datix database for any serious incidents related to the use of AnMach.

The remaining sections refer to this option II = we cannot label charts as AnMach (more likely to be the case).

The Methods for Phase 1 of this study can be broken down into the following sections:

1. Identification of study participants:

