This involves applying the inclusion criteria listed above to patients admitted to 2NA and main recovery between the 1st April 2020 and 1st June 2020. The list of these patients will be generated using the records from the Cerner EPR Computer System where all patient locations within the hospital are updated in a 'live' fashion. This will give us an accurate picture of all the patients admitted to 2NA and main recovery during the above period thus providing a population of patients who were exposed to ventilation by AnMach. In order to identify individuals who were ventilated by AnMach while in this location, we will review the nursing charts and the physiotherapy notes which we anticipate will provide evidence for the method ventilating a particular patient in that location of the hospital

2. Review of raw data:

Following identification of study participants using the inclusion criteria (Section 8.1.1), data from their admission will be reviewed and collected. This will involve manual review of the following:

- Observation charts (when released for review). These provide quantitative data and trends can be identified to provide evidence that ventilatory support was being weaned or escalated:
 - These charts will show hour by hour trends in the level of respiratory support being delivered to the patients, including; the mode of ventilation, the delivered oxygen concentration, the pressure settings of ventilation, position of the patient (i.e. whether prone or not).
 - They also show the physiological status of the patient including their hourly observations and regular blood gas sampling, thus providing evidence about

- whether the patient was deteriorating, improving or remaining static in terms of ventilatory support.
- The chart may also provide qualitative evidence of a patient weaning from ventilation. The back of the chart provides space for the nursing staff to record information regarding the course of the day using 'free-hand'. This will provide evidence of the ventilator being used as well as the clinical direction of the patient i.e. whether weaning or not.
 - Daily review sheets filled in by ICU clinicians and physiotherapists.

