 - These will provide more information about the progress of patients while being ventilated. There may be documentation that mentions difficulties that have arisen when ventilating or weaning ventilation in these patients as well as providing indications as to why patients have been switched to different modes of ventilation or device.
 - Physiotherapists' notes may help us to identify the AnMach patients.

3. Data recording and translation to Outcomes/Endpoints

The data for each patient will be recorded and anonymised in an encrypted Excel spread sheet and will include:

- Age, gender
- Reason for admission
- APACHE II score
- SOFA score
- Date of admission to ICU
- Date of intubation
- Was patient ventilated using AnMach?
- Number of days of ventilatory support before weaning ventilation
- Number of days spent weaning from ventilation to being successfully weaned from ventilator (extubation)
- Was patient transferred from AnMach onto conventional ICU ventilator?
- How many days following ventilation with the AnMach did the transfer happen?
- What was the indication for transferring a patient from an AnMach to the conventional ICU ventilator?
- Did the patient receive a tracheostomy?
- Adverse events possibly correlated with the use of AnMach: soda lime issues, gas flow issues, hypoxia, elevate pressure of ventilation, water need to be cleaned out of tubes, sudden respiratory rate increase, need for manual ventilation
- Organ support - number of days of
 - Use of one or more inotropic drugs or anti arrhythmic

- Renal - a need for renal replacement therapy
- Liver - correction of coagulopathy (plasma use), hypoglycaemia (glucose use), presence of hyperlactataemia (high lactate levels) related to liver failure
- Neuro - delirium
- Date of discharge from ICU or date of death
- Length of ITU stay

The above data will be used to identify quantitative values for the primary and secondary endpoints discussed in section 13.1. This will then be analysed as discussed in Section 13.0

9.1.1b - a prospective data collection

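### Anaesthetic-machine status and outcomes are read from overlapping records and the denominator is not settled, so the primary proportions may be inflated or diluted depending on which cohort is used

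*Protocol*

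**What the plan says.** **How exposure is established.** Protocol 8.1.1 (Phase 1 inclusion) requires AnMach ventilation "as suggested by daily nursing observation charts and daily review sheets in the notes of ICU clinicians and physiotherapists". Section 9.1.1a takes the candidate list from Cerner location records for 2NA and main recovery. To find the individuals on an AnMach within that list, "we will review the nursing charts and the physiotherapy notes which we anticipate will provide evidence for the method ventilating a particular patient". Of the free-hand text on the back of the nursing chart it says: "This will provide evidence of the ventilator being used as well as the clinical direction of the patient". It adds that physiotherapists' notes may help to identify these patients. No equipment log or bed-to-machine record is named, and the protocol warns that "it may not be possible to tell from the documentation which patients were ventilated with AnMach versus a conventional ITU ventilator".

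**How outcomes are found.** Of the daily review sheets completed by clinicians and physiotherapists, 9.1.1a says: "There may be documentation that mentions difficulties that have arisen when ventilating or weaning ventilation in these patients". The same sheets are expected to explain why a patient changed mode or device. Of the observation charts it says: "These charts will show hour by hour trends in the level of respiratory support being delivered to the patients".

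**Which patients count.** Section 9.1.1a sets out two options and states that the sections after it follow Option II, in which devices cannot be told apart and adverse events are recorded for everyone admitted to the two locations. Section 13.2 nevertheless lets the number of available charts identified as AnMach use determine the cases analysed.

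**Primary endpoints (13.1.1).** The first is the proportion of patients with any of a list of adverse events. The second is weaning failure while on an AnMach: no reduction in support for more than 48 hours, or transfer to an ITU-grade ventilator.

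**The concern.** Two weaknesses meet here.

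First, one entry can do two jobs. A note that a patient was moved from an AnMach to an ITU ventilator shows that the patient was on an AnMach and also scores a weaning failure. A note of a soda lime problem does the same for the adverse-event endpoint, since 5.1 describes soda lime as part of the AnMach rebreathing system and ITU ventilators as non-rebreathing. A patient ventilated without incident produces neither entry. If such patients are recognised less often, they drop out of the denominator while patients with events stay in.

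Second, the protocol does not say whether the denominator is the recognised AnMach patients or everyone in the two locations. The possible bias differs between the two: selection on outcome in the first, dilution by patients on ITU ventilators in the second.

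These two proportions are the main quantitative result, from at most 15 datasets (3.0), so a few charts in or out change what is reported. Once a restricted cohort has been formed, analysis of the selected charts alone cannot show who was left out.

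**Working it through.** The protocol gives no expected rate, sample size or power, so there is no figure to reproduce. The check is to set the sections side by side and then see what each denominator does to a proportion.

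**1. The denominator**

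| Place | Who is counted |
|---|---|
| 9.1.1a, Option II | All patients admitted to 2NA and main recovery |
| 8.1.1, Phase 1 | Only patients whose records suggest AnMach ventilation |
| 9.1.1a, step 1 | Location list, then individuals identified as on an AnMach |
| 13.1.1, first endpoint | Patients, not further specified |
| 13.1.1, second endpoint | Patients on an AnMach, so device status is needed |
| 13.2 | Available charts identified as AnMach use; only adverse events if charts cannot be identified |

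These do not define one population. The second endpoint also cannot be scored in full under an option in which the device is unknown.

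**2. Cohort restricted to recognised charts**

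Let p be the true proportion with the outcome among AnMach patients, s1 the probability that a patient with the outcome is recognised as AnMach, and s0 the same for a patient without it. Then

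observed = p·s1 / (p·s1 + (1 − p)·s0).

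All three inputs are assumptions. With p = 0.40:

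| s1 | s0 | Calculation | Observed |
|---|---|---|---|
| 0.7 | 0.7 | 0.28 / (0.28 + 0.42) | 0.400 |
| 1.0 | 0.8 | 0.40 / (0.40 + 0.48) | 0.455 |
| 1.0 | 0.5 | 0.40 / (0.40 + 0.30) | 0.571 |
| 0.9 | 0.3 | 0.36 / (0.36 + 0.18) | 0.667 |
| 0.6 | 0.8 | 0.24 / (0.24 + 0.48) | 0.333 |

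Equal recognition gives no bias. The proportion rises when s1 exceeds s0 and falls when it is lower.

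In whole patients at the stated maximum: 6 of 15 is 40% (exact 95% CI 16% to 68%). If 4 of the 9 without the outcome are not recognised, the result is 6 of 11, or 55% (23% to 83%).

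**3. Whole-location denominator (adverse events)**

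Let f be the share of location patients on an AnMach and q the rate of the listed events in the others. Then

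observed = f·p + (1 − f)·q.

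With p = 0.40, again all assumed:

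| f | q = 0 | q = 0.2 | q = 0.4 |
|---|---|---|---|
| 0.75 | 0.30 | 0.35 | 0.40 |
| 0.50 | 0.20 | 0.30 | 0.40 |

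The proportion is diluted when q is below p and unchanged when they are equal. It is inflated only if q exceeds p: for p = 0.20, f = 0.5 and q = 0.4, it is 0.10 + 0.20 = 0.30.

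**The case against.** A reader might infer that both primary proportions are inflated. The documents do not support that, for four reasons.

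- **Option II.** It is declared to govern the later sections and keeps every location patient in the adverse-event count. An uneventful patient is then not lost, and dilution is the likelier error. This stands for the first endpoint as far as Option II is applied, but 8.1.1, 9.1.1a step 1 and 13.2 condition on identification again. It does not help the second endpoint, which needs device status.
- **Direction.** Nothing says that uneventful AnMach patients are less well documented. AnMach tasks described in the background (5.1), such as 24-hourly testing and 4-hourly increases in fresh gas flow, would identify uneventful patients if charted. Under-recording of events could also pull the proportions down. This stands.
- **Sources.** They are not only free text. Hypoxia, raised pressure, respiratory rate and the 48-hour criterion may be readable from hourly data and do not reveal the device. This stands in part. The hourly items listed are mode, oxygen concentration, pressures and position, without the device, and Cerner gives location and not machine.
- **Sequence.** Section 9.1.1a places identification before data review, and no section says the same individuals do both. This is fair, but the list is not locked. Physiotherapy notes are still offered as a means of identification in the review step, and the AnMach question sits on the same extraction sheet as the events. That field may mean unconfirmed patients are also recorded, so it is not certain that they would be lost.

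The analysis is descriptive and the documentation limit is openly stated. That lowers the stakes but leaves the denominator open.

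**Conclusion.** The point holds in a conditional form. Exposure and outcomes come from overlapping records, no event-independent record of the device is named, and the protocol gives conflicting denominators. If analysis is confined to recognised charts, inclusion may depend on outcome and the primary proportions may be inflated. The case is clearest for the transfer component of weaning failure, where the same entry establishes both exposure and failure. If all location patients are counted, the adverse-event proportion may be diluted instead.

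The documents fix neither direction nor size. On the assumed inputs, a true 40% could be reported as anything from 33% to 67% in a restricted cohort, and from 20% to 40% in a whole-location one. Upward bias needs s1 greater than s0; dilution needs q below p. With at most 15 datasets, four misplaced patients move the result by 15 percentage points, so this should be settled before charts are abstracted.

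**What to change.** In 8.1.1 (Phase 1), 9.1.1a and 13.2:

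1. Classify every intubated patient on the Cerner location list as AnMach, ITU ventilator or undetermined. Lock that classification before any event is abstracted.
2. Record its basis in one column: a routine device-specific chart entry; only a note of a problem or transfer; location only or undetermined. Location must not count as identification, because every candidate qualifies by location.
3. Report the adverse-event proportion for (a) patients identified by routine entries, (b) all identified AnMach patients, and (c) all intubated location patients not shown to be on an ITU ventilator.
4. Report weaning failure for (a) and (b) only, since transfer from an AnMach cannot be scored where the device is unknown. Give the number undetermined and, as a bound, add them to the denominator as non-transfers. In the example above, 6 of 11 (55%) with four undetermined would be shown beside 6 of 15 (40%).

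The cost is protocol wording, one spreadsheet column, a little more abstraction and a few table rows. Set (c) may include patients who were never on an AnMach, so it serves only as a bound and not as the main estimate.

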9.2 PHASE 2 PROCEDURES: qualitative study, survey and interviews

9.2.1 PARTICIPANT RECRUITMENT PROCESS

All participants who wish to enter the study will be fully screened and consented by the Chief Investigator, or one of the qualified clinicians involved in the study as Clinical Co-investigator.

The Survey

A structured questionnaire will be developed by the study team. The questionnaire will be hosted by the Qualtrics platform (<https://www.qualtrics.com/uk/>), a service provided to academics with a stricter privacy policy compared to more frequently used survey platforms. The survey will be a mean of screening ITU professionals. The participants will be asked to answer the following questions:

Qualification: nurse, physiotherapist, intensivist not anaesthetist, anaesthetist
Years of ITU experience

Did you look after a patient ventilated on anaesthetic machine during your time on 2NA/main recovery?
Have you ever ventilated a patient on an anaesthetic machine before this event?
Were you aware of any guidance for ventilating patients using anaesthetic machines?
Have you experienced any problems with ventilating patients on anaesthetic machine? - if yes please describe
Would you consent to be interviewed about your experience using anaesthetic machines?

The first page of the survey will include information accompanying the questionnaire fully explaining the purpose of the research and what the data collected would be used for.

The in-depth interviews

In the second phase of the study, in-depth interviews with 12 (minimum) to 20 (maximum) ITU professionals will be performed. Study participants who volunteer to be interviewed will be contacted on the phone or via a video call platform (e.g. Zoom or Microsoft Teams) and asked for their availability for a thirty minutes interview. The interview will be recorded and later transcribed. Interviewees will be asked to record their consent before beginning the interview. The topic guide for interviews and the answers to the survey will guide the interviews. The main topic will be the professionals experience of managing a patient on anaesthetic machines: easiness, adverse events, solutions, recording of events, impact on their mental health.

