7.1 METHODS

This project consists of two parallel phases:

Phase 1, a quantitative, observational, cohort study to detect the effect of exposure to anaesthetic machine ventilation of COVID-19 patients in term of adverse events.

The quantitative phase may be also divided in two parts:

1a, a retrospective data collection of patients admitted to RFH ITU (and possibly the Barnet Hospital ITU) and connected to anaesthetic machines between the 1st April and 1st June 2020, and

1b, a prospective data collection of cases that occur between the 1st June and the 30th October 2020 in order to cover a new period of possible COVID-19 surge.

Phase 2, a survey and an interview stage engaging ITU professionals that managed patients on anaesthetic machines during the COVID-19 surge in an unfamiliar environment (nurses, physiotherapists, and doctors).

Mixed methods were chosen to integrate elements of quantitative and qualitative research in order to achieve a broader understanding of the topic. Also using both methods and integrating results helps determining the interview phase sample and interpreting the findings of the quantitative phase (O'Cathain et al., 2007).

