13.2 STATISTICAL ANALYSIS PLANS

The retrospective (and prospective, if available) data collection:

This is a cohort study with no sample size calculation. The number of patients managed on AnMach and charts available (identified as AnMach Use) will dictate how many cases we will be able to analyse. The statistical analysis will be descriptive and performed with the Microsoft Office Excel data analysis package in case we will not be able to identify the AnMach charts and we will collect only adverse events data and report them as proportions. The clinical outcomes will be described using absolute and relative frequencies (expressed as a percentage) or position indices (average or median) and relative dispersion indices (standard deviation or interquartile range) suitable for the type of variable analysed. If comparison between AnMach patients and ITU ventilator patients will be possible, mean and standard

23

deviation of clinical outcomes for the two groups will be compared (the plan for this analysis will be explained in case of requesting a protocol amendment).

The Survey:

The questionnaire answers will be inserted in an excel spreadsheet and cleaned. Incomplete, inaccurate and missing data will be detected and discussed during interviews. The results will be used to select participants for the second stage and implement the topic guide for interviewing the volunteers. For this aspect of the study the statistical analysis will be descriptive and performed with the Microsoft Office Excel data analysis package. Data will be reported as proportions.

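### The survey's only question about problems has no ward or period limit, so its reported proportion and the interview topic guide can mix surge problems with earlier ones

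*Protocol*

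**What the plan says.** Section 9.2.1 (The Survey) says that the questionnaire is still to be written ("A structured questionnaire will be developed by the study team") but already lists its questions. After profession and years of ITU experience come four content items, then consent to interview. The four are, in order:

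1. Exposure: "Did you look after a patient ventilated on anaesthetic machine during your time on 2NA/main recovery"
2. Earlier use: "Have you ever ventilated a patient on an anaesthetic machine before this event"
3. Guidance: "Were you aware of any guidance for ventilating patients using anaesthetic machines"
4. Problems: "Have you experienced any problems with ventilating patients on anaesthetic machine", with a request to describe them if yes.

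The profession item reads "Qualification: nurse, physiotherapist, intensivist not anaesthetist, anaesthetist", so anaesthetists may answer. Section 7.1 gives the target of Phase 2 as staff who "managed patients on anaesthetic machines during the COVID-19 surge in an unfamiliar environment". The Phase 2 inclusion criteria (under Section 8.2) set the place and period as the RFH ITU from 1 April to 30 October 2020. Under Section 13.2 the survey is analysed descriptively and given as proportions. That section adds: "The results will be used to select participants for the second stage", and says that the results also inform the topic guide.

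**The concern.** The exposure item is anchored to the surge wards and the problems item is not. A respondent who used these machines before the surge, for instance an anaesthetist in theatre, can answer yes because of that earlier use. Section 5.1 treats long-term ventilation on these machines as off-label, so problems met in ordinary anaesthetic practice belong to a different exposure.

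The primary aim in Section 6.1 is to find issues with ventilating critically ill patients on these machines that the guidelines do not describe. This is the only survey item that bears on that aim. If its yes answers mix two exposures, the reported percentage does not describe the surge, and interview prompts may be built on problems from another setting.

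**Working it through.** There is no sample size, power or test to reproduce, and the documents give no figure for this item. The check sets the text side by side and adds one illustration under stated assumptions.

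**Step 1. Setting limit of each item (Section 9.2.1).**

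| Item | Place | Period |
|---|---|---|
| Exposure | 2NA/main recovery | the respondent's time there |
| Earlier use | any | before the surge |
| Guidance | none given | none given |
| Problems | none given | none given |

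Only one item asks about earlier use, and the guidance item stands between it and the problems item.

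**Step 2. What the existing items can separate.** Cross the exposure and earlier-use answers for respondents who report a problem:

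| Exposure | Earlier use | Source of the reported problem |
|---|---|---|
| yes | no | not pre-surge |
| no | yes | not from 2NA/main recovery, and may be pre-surge |
| yes | yes | undetermined, unless the free text shows when or where |
| no | no | use elsewhere in the study period, or an inconsistent answer |

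Restricting the denominator to exposed respondents would remove the second and fourth rows. The third row stays mixed, because the free-text prompt does not ask for date or ward. The Protocol states no such restriction. A later reporting rule could add one, but it could not supply a setting that the question never asked for.

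**Step 3. Where the answer goes.** Section 13.2 sends it to a reported proportion and to the topic guide. The Phase 1 primary endpoints (Section 13.1.1) come from patient charts. The Phase 2 endpoint (Section 13.3.1) is a proportion of interviewees. Neither is computed from this item.

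**Step 4. Illustration of size.** Let p be the true share of respondents with a surge problem and f the share with earlier use, taken to be the same among those without a surge problem. Let q be the chance that an earlier user without a surge problem answers yes because of an earlier one. Then

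observed yes share = p + (1 − p) × f × q.

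None of p, f or q is in the documents. With p assumed to be 40%:

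- f = 10%, q = 30%: 0.40 + 0.60 × 0.10 × 0.30 = 41.8%, an excess of 1.8 points
- f = 50%, q = 50%: 0.40 + 0.60 × 0.50 × 0.50 = 55%, an excess of 15 points
- f = 80%, q = 50%: 0.40 + 0.60 × 0.80 × 0.50 = 64%, an excess of 24 points

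With f = 0 the excess is zero. The spread shows only that the result depends on who answers the survey. It is not an estimate.

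**The case against.** The strongest reply is that respondents will read the item as the authors meant it. The survey's first page explains the purpose of the research, the content items open with the surge wards, and the earlier-use item refers to the surge as the event. Sections 5.1 and 5.2 also suggest that the intended ITU staff had little experience with this equipment. Section 13.2 plans to take up inaccurate answers at interview. And the questionnaire is not final.

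Much of this stands, and it limits the point to what may happen. It does not remove it. The wording asks about any problems, anaesthetists may answer, and follow-up at interview reaches only the 12 to 20 people interviewed. The Phase 2 criteria describe the consultants among them as not accredited anaesthetists, so the respondents most likely to have theatre experience are the least likely to be followed up.

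A reader might infer more than the text supports:

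- *That pre-surge problems are counted as surge problems.* The documents show only that they can be.
- *That the two cannot be separated afterwards.* They can in part, as Step 2 shows.
- *That item order primes the answer.* The guidance item intervenes, and only one item concerns earlier use.
- *That this item decides who is interviewed.* Section 13.2 says that survey results select participants but names no item. The stated criteria are profession, care of patients on these machines in the study period, and consent, so a pre-surge yes cannot by itself make anyone eligible.

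**Conclusion.** The concern holds in a limited form. The problems item lacks the setting limit that the exposure item has, in a survey that expects some respondents to have earlier experience. The descriptive proportion, and the topic guide built from the answers, can therefore mix surge and earlier problems, with only partial means of separating them. No chart or interview endpoint is directly affected, and an effect on interviewee selection is possible but not shown. The size cannot be derived from the documents; the 1.8 to 24 point excess in the illustration rests wholly on assumed shares. This is a minor point, worth correcting because the correction is so cheap.

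**What to change.** Limit the problems item to the Phase 2 eligibility setting and period, for example: *While caring for patients at the RFH ITU (including 2NA/main recovery) since 1 April 2020, did you experience any problems ventilating a patient on an anaesthetic machine? If yes, please describe.* The survey runs in July 2020 (Section 11), so no end date is needed in the question.

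Word the exposure item to the same setting, and report the problems proportion among those who answer yes to it. Limiting both items to 2NA/main recovery alone would be too narrow: eligibility covers the RFH ITU, and staff who used the machines elsewhere in the unit would be missed. If the team needs to know who worked on 2NA/main recovery, as Section 6.2 suggests, the answer options of the exposure item can record it.

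The cost is two wording changes and one stated denominator in a questionnaire that is not yet final. No item is added. The small downside is that problems from other settings are no longer captured.

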13.3.1 Phase 2 ENDPOINTS

The interviews phase aims to detect the proportion of interviewees who experienced difficulties of managing patients with an AnMach and feeling stressed or overwhelmed by the situation.

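### The Phase 2 proportion is drawn from survey-guided interviews with no endpoint question put identically to every interviewee, so it may partly reflect the questioning

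*Protocol*

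**What the plan says.** Section 13.3.1 of the protocol states the Phase 2 endpoint as a count: "The interviews phase aims to detect the proportion of interviewees who experienced difficulties of managing patients with an AnMach", together with feelings of stress or overload. The data come from 12 to 20 interviews of thirty minutes each (9.2.1).

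On how the interviews are run, section 9.2.1 says: "The topic guide for interviews and the answers to the survey will guide the interviews". It then names the main subjects without limiting them to any group of interviewees: "easiness, adverse events, solutions, recording of events, impact on their mental health".

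One survey item lies close to the endpoint: "Have you experienced any problems with ventilating patients on anaesthetic machine? - if yes please describe". The survey has no item on stress.

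Section 13.2 gives the survey two roles in the interviews: "The results will be used to select participants for the second stage and implement the topic guide for interviewing the volunteers". It adds: "Incomplete, inaccurate and missing data will be detected and discussed during interviews". Section 11 runs the survey from 1 to 31 July 2020 and starts the interviews on 15 July.

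**The concern.** Letting a survey inform interviews is ordinary and useful when the aim is thematic depth. The difficulty arises because section 13.3.1 also takes a proportion from the same interviews. A proportion is interpretable only if each person in the denominator had a comparable chance of being counted. Here the conversation is guided partly by earlier answers, one of which concerns nearly the same matter as the endpoint, and only a positive answer to that item produces text to follow up.

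An interviewee who described a problem in the survey may therefore be probed on it in more depth than one who did not. The reported proportion could then differ from what uniform questioning would have given, and a reader could not separate staff experience from interview conduct.

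**Working it through.** **1. Number of interviews.** Section 6.2 sets four professional groups of 3 to 5 people. 4 × 3 = 12 and 4 × 5 = 20, which reproduces the 12 to 20 in section 9.2.1.

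**2. Weight of one interviewee.** 1/12 = 8.3 percentage points and 1/20 = 5.0 points. One person classified differently moves the proportion by that much, up or down.

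**3. Where questioning can differ between interviewees.**
- *Through the person's own survey answers.* Section 9.2.1 does not say whether it means the interviewee's own answers or the pooled ones. Two things favour the individual reading. The topic guide and the survey answers are named as separate guides, although pooled results already enter through the topic guide. And discussing a respondent's incomplete or missing answers requires that person's questionnaire.
- *Through the topic guide.* If only pooled answers are meant, the survey still shapes the guide. Interviews and survey overlap from 15 to 31 July, that is 31 − 15 + 1 = 17 days, so the guide could differ between early and late interviewees.
- *What is common to all.* Five broad subjects, including easiness and mental health. These are subjects, not a fixed question. No section requires the endpoint to be asked in the same words of everyone.
- *Which part of the endpoint is exposed.* Mainly difficulties. With no stress item in the survey, no matching answer can steer the stress part; that part lacks only the common question.

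**4. Illustration of size, on assumed inputs.** The protocol gives no expected proportion or disclosure rate. Let s be the share of interviewees who reported a problem in the survey, q the true share with difficulties among the rest, and d the chance that such a person discloses it without specific probing. Assume that everyone who reported a problem is a true positive and is counted. Then:

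- true proportion = s + (1 − s)q
- observed proportion = s + (1 − s)qd
- understatement = (1 − s)q(1 − d)

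With s from 0.3 to 0.7 and q from 0.3 to 0.5:

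| d | Smallest (s = 0.7, q = 0.3) | Largest (s = 0.3, q = 0.5) |
|---|---|---|
| 1 | 0 points | 0 points |
| 0.8 | 0.3 × 0.3 × 0.2 = 1.8 points | 0.7 × 0.5 × 0.2 = 7.0 points |
| 0.5 | 0.3 × 0.3 × 0.5 = 4.5 points | 0.7 × 0.5 × 0.5 = 17.5 points |
| 0 | 0.3 × 0.3 × 1 = 9.0 points | 0.7 × 0.5 × 1 = 35.0 points |

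The last row would need people who reported no problem never to be led to the subject. The common subjects in 9.2.1 speak against that, so it is an outer limit only. The direction is also built in: the model allows no false positives. If probing turned minor remarks into counted difficulties, the error would run upwards.

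**5. Sampling error for scale.** The exact 95% interval for an observed 50% is 21% to 79% with n = 12 and 27% to 73% with n = 20.

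**The case against.** A reader might infer that staff who reported a problem are probed on it and the others are not, so that the proportion is understated by a definite amount. The protocol does not support that. Its listed subjects hold for all interviewees, and easiness and mental health plainly touch both parts of the endpoint. That each interview follows the person's own answers is an inference. The one clearly individual carry-over, in 13.2, directs attention to blank or doubtful answers, not to clear reports of a problem. This objection stands: unequal depth of probing is a risk, not a stated rule.

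It can also be said that every interviewee has already answered one uniform question on problems in the survey, which 13.2 reports as proportions. That is true and helpful, but it covers ventilation problems only, and it is not the proportion that 13.3.1 says the interviews will give.

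A sharper objection is aimed at the remedy. Take 16 interviewees, of whom 8 reported a problem in the survey, and suppose 60% of the other 8 truly had difficulties. The true proportion is (8 + 8 × 0.6)/16 = 80%. If open interviewing uncovers half of the hidden cases, the result is (8 + 8 × 0.6 × 0.5)/16 = 65%. If a closed question merely draws the same denial again and nothing else counts, it is 8/16 = 50%, further from the truth. This stands as a warning against discarding what the open part reveals, and the fix allows for it.

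Finally, the planned interview analysis is thematic (13.3), no test or decision hangs on the proportion, and sampling error is wide. That lowers the severity. It does not remove the point, because uneven ascertainment is systematic and comes on top of sampling error.

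**Conclusion.** The point holds in a limited form. The endpoint in 13.3.1 is a proportion. The interviews behind it are guided by survey answers and by a topic guide that survey results can still be shaping after interviewing has begun. Nothing makes the endpoint question the same for every interviewee, so the proportion may partly reflect how people were questioned, mainly in its difficulties part.

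The protocol does not allow the size or direction of any distortion to be computed. The illustrative 0 to 35 points rest wholly on assumed values and on a model that permits only understatement, and the upper end needs a silence that the protocol does not prescribe. What follows from its own figures is only the weight of one person, 5.0 to 8.3 points. Selection of interviewees by survey results is a separate matter and is not counted here. Severity is low: this is an inexpensive improvement to a count, not a flaw in the qualitative work.

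**What to change.** - **Section 9.2.1:** add that every interview opens with the same two questions, in the same words, before any survey answer is mentioned: one on difficulty managing a patient on an AnMach, one on having felt stressed or overwhelmed.
- **Section 13.3.1:** add that the reported proportions are taken from those two answers, and that interviewees whose difficulty or stress came out only in the later open part are reported separately, so that no disclosure is lost.
- **Unchanged:** survey-guided probing and the developing topic guide stay in use for the open part and the thematic analysis.

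This works whether 9.2.1 means the interviewee's own survey answers or the pooled ones. It costs one to two minutes of a thirty-minute interview, a short addition to each of the two sections, and some priming of the open conversation by the opening questions.
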